**PAGE 84/139** 

• BTX for any urological condition, e.g. detrusor or urethral sphincter treatments (exclusion criterion #11).

Prohibited in the 6 months prior to Screening and throughout the study:

• Capsaicin or resiniferatoxin (exclusion criterion #14).

Prohibited in the 3 months prior to Screening and throughout the study:

- BTX for any non-urological condition (exclusion criterion #12)
- Bladder installation with any pharmacologic agent (exclusion criterion #13).

Prohibited in the 4 weeks prior to Screening and throughout the study:

- Indwelling bladder catheter (exclusion criterion #10)
- Any neuromodulation/electrostimulation usage for urinary symptoms/incontinence (exclusion criterion #15)

- Any new investigational drug or device (exclusion criterion #27).
- 6.4.2.1 Concomitant treatment for Neurogenic Detrusor Overactivity

These data are to be collected at Screening and at other timepoints. In particular, the following should be collected:

- Daily CIC frequency (at Screening, and if there is a clinically significant change in frequency postbaseline)
- Current anticholinergic or beta-3 agonist usage (at Screening, and if there is a change in medication/frequency/dosage postbaseline).

PAGE 85/139

### 7 ASSESSMENT OF EFFICACY

For the timing of assessments in this study, refer to the schedules in Table 4, Table 5, and Table 19.

## 7.1 Primary Efficacy Endpoint and Evaluations

See Section 3.2.1.

## 7.2 Secondary Efficacy Endpoints and Evaluations

See Section 3.2.2 and Table 19.

Table 19 Efficacy Endpoints During Initial Treatment and Retreatment

Measure	Planned timepoints (dependent on timing of retreatments)	Variable	Endpoint
Weekly number of urinary incontinence episodes on 7-day bladder diary	Study Baseline (Screening) or treatment cycle baseline Week 2 Week 6 Week 12 Every 12 weeks thereafter until retreatment EOS Visit.  Study Baseline  Study Baseline  Weekly number of urinary incontinence episodes  Proportion of episodes of urincontinence is achieved) a proportion of urinary incontinence is achieved at several lev improvement improvement improvement improvement timepoint  Study Baseline  Total daily urinary  Mean change baseline to eat timepoint with cycle in week urinary incontinence is achieved at incontinence i		baseline to each subsequent timepoint within the treatment cycle in weekly number of urinary incontinence episodes  • Proportion of subjects with no episodes of urinary incontinence (i.e. continence is achieved) at each timepoint  • Proportion of subjects with a urinary incontinence response at several levels (i.e. ≥30% improvement, ≥50% improvement, ≥75% improvement etc.) at each
Total daily urinary frequency (CIC and spontaneous voiding) on 7-day bladder diary	Study Baseline (Screening) or treatment cycle baseline Week 2 Week 6 Week 12 Every 12 weeks thereafter until retreatment EOS Visit	Total daily urinary frequency	Mean change from study baseline to each subsequent timepoint within the treatment cycle in total daily urinary frequency
Daily spontaneous voiding frequency on 7-day bladder diary	Study Baseline (Screening) or treatment cycle baseline Week 2 Week 6 Week 12 Every 12 weeks thereafter until retreatment EOS Visit.	Daily spontaneous voiding frequency	Mean change from study baseline to each subsequent timepoint within the treatment cycle in daily spontaneous voiding frequency

PAGE 86/139

Measure	Planned timepoints (dependent on timing of	Variable	Endpoint
Daily CIC frequency on 7-day bladder diary	retreatments) Study Baseline (Screening) or treatment cycle baseline Week 2 Week 6 Week 12 Every 12 weeks thereafter until retreatment EOS Visit.	Daily CIC frequency	Mean change from study baseline to each subsequent timepoint within the treatment cycle in daily CIC frequency
Total 24-hour voided volume on 1 day of 7-day bladder diary (CIC and spontaneous voiding)	Study Baseline (Screening) or treatment cycle baseline Week 2 Week 6 Week 12 Every 12 weeks thereafter until retreatment EOS Visit.	Total 24-hour voided volume	Mean change from study baseline to each subsequent timepoint within the treatment cycle in total 24-hour voided volume
24-hour voided volume on 1 day of 7-day bladder diary (spontaneous voiding only)	Study Baseline (Screening) or treatment cycle baseline Week 2 Week 6 Week 12 Every 12 weeks thereafter until retreatment EOS Visit.	24-hour voided volume (spontaneous voiding only)	Mean change from study baseline to each subsequent timepoint within the treatment cycle in 24-hour voided volume (spontaneous voiding only)
24-hour voided volume on 1 day of 7-day bladder diary (CIC only)	Study Baseline (Screening) or treatment cycle baseline Week 2 Week 6 Week 12 Every 12 weeks thereafter until retreatment EOS Visit.	24-hour voided volume (CIC only)	Mean change from study baseline to each subsequent timepoint within the treatment cycle in 24-hour voided volume (CIC only)

PAGE 87/139

Measure	Planned timepoints	Variable	Endpoint	
Tribusui C	(dependent on	, mimore	Enupoint	
	timing of			
	retreatments)			
Total volume per void (spontaneous and CIC) on 1 day of 7-day bladder diary	Study Baseline (Screening) or treatment cycle baseline Week 2 Week 6 Week 12 Every 12 weeks thereafter until retreatment EOS Visit.	Total volume per void	Mean change from study baseline to each subsequent timepoint within the treatment cycle in total volume per void	
Volume per void (spontaneous voiding only) on 1 day of 7-day bladder diary	Study Baseline (Screening) or treatment cycle baseline Week 2 Week 6 Week 12 Every 12 weeks thereafter until retreatment EOS Visit.	Volume per void (spontaneous voiding only)	Mean change from study baseline to each subsequent timepoint within the treatment cycle in volume per void (spontaneous voiding only)	
Volume per void (CIC only) on 1 day of 7-day bladder diary	Study Baseline (Screening) or treatment cycle baseline Week 2 Week 6 Week 12 Every 12 weeks thereafter until retreatment EOS Visit.	Volume per void (CIC only)	Mean change from study baseline to each subsequent timepoint within the treatment cycle in volume per void (CIC only)	
MCC measured by urodynamic filling cystometry Urodynamic subset only	Study Baseline (Screening), Week 6	MCC	Mean change from study Baseline to Week 6 after each treatment in MCC	
MDP during storage measured by urodynamic filling cystometry Urodynamic subset only	Study Baseline (Screening), Week 6	MDP	Mean change from study Baseline to Week 6 after each treatment in MDP	
Vol@1stIDC measured by urodynamic filling cystometry Urodynamic subset only	Study Baseline (Screening), Week 6	Vol@1stIDC	Mean change from study Baseline to Week 6 after each treatment in Vol@1stIDC	

PAGE 88/139

Measure	Planned timepoints (dependent on timing of retreatments)	Variable	Endpoint
PdetMax@1stIDC measured by urodynamic filling cystometry Urodynamic subset only	Study Baseline (Screening), Week 6	PdetMax@1stIDC	Mean change from study Baseline to Week 6 after each treatment in PdetMax@1stIDC
Presence of IDCs measured by urodynamic filling cystometry Urodynamic subset only	Study Baseline (Screening), Week 6	Presence of IDCs	Proportion of subjects with no IDCs on urodynamic assessment (i.e. urodynamic cure is achieved) after each treatment
EFP measured by urodynamic filling cystometry Urodynamic subset only	Study Baseline (Screening), Week 6	EFP	Mean change from study Baseline to Week 6 after each treatment in EFP
DC measured by urodynamic filling cystometry Urodynamic subset only	Study Baseline (Screening), Week 6	DC	Mean change from study Baseline to Week 6 after each treatment in DC
Treatment response according to I-QoL total and domain summary score	Study Baseline (Treatment Visit) or treatment cycle baseline Week 6 Week 12 EOS Visit.	I-QoL total summary and domain score	Mean change from study baseline to each subsequent timepoint within the treatment cycle in I-QoL total summary and domain score
Treatment response according to EQ-5D-5L	Study Baseline (Treatment Visit) or treatment cycle baseline Week 6 Week 12 EOS Visit.	EQ-5D-5L score	Mean change from study baseline to each subsequent timepoint within the treatment cycle in EQ-5D-5L score

PAGE 89/139

Measure	Planned timepoints (dependent on timing of	Variable	Endpoint
Treatment response according to mPGI-I score	retreatments)  Week 2  Week 6  Week 12  Every 12 weeks thereafter until retreatment  EOS Visit.	mPGI-I score	Mean mPGI-I score at each timepoint following each IMP administration
Duration of effect measured by time from previous treatment until next treatment requested	• Treatment Visit (Day 1) until date of request of first retreatment (for first treatment cycle)	Time to request retreatment	
 
Mean number of days before retreatment is requested
 
Median number of days before retreatment is requested
 

(if subsequently found to be eligible for retreatment)	• Retreatment Visit until date of request of next retreatment (for second and subsequent treatment cycles)		
Duration of effect measured by time from previous treatment until subject is confirmed eligible for next treatment	Treatment Visit (Day 1) until date subject is confirmed as eligible for retreatment (for first treatment cycle) Retreatment Visit until date subject is confirmed as eligible for next retreatment (for second and subsequent treatment cycles)	Time to eligibility for retreatment	Mean number of days before eligible for retreatment     Median number of days before eligible for retreatment
Duration of effect measured by time between two treatment administrations	Treatment Visit (Day 1) until first Retreatment Visit (for first treatment cycle) Retreatment Visit until next retreatment visit (for second and above treatment cycles)	Time between treatments	
 
Mean number of days between two treatment administrations
 
Median number of days between two treatment administrations
 

CIC=clean intermittent catheterisation; DC=detrusor compliance; EFP=end fill pressure; EOS=end of study; EQ-5D-5L=EuroQol 5-dimension 5-level; IDC=involuntary detrusor contraction; IMP=investigational medicinal product; I-QoL=incontinence quality of life; MCC=maximum cystometric capacity; MDP=maximum detrusor pressure; mPGI-I=modified patient global impression – improvement; PdetMax@1stIDC=maximum detrusor pressure at first involuntary detrusor contraction; Vol@1stIDC=volume at first involuntary detrusor contraction.

PAGE 90/139

#### 7.3 Methods and Timing of Assessing, Recording, and Analysing Efficacy Data

Methods for assessing efficacy data are described below. Timing of efficacy assessments are discussed in Section 5. Procedures for recording efficacy data are discussed in Section 13.1, and methods of analysis are discussed in Section 9.4.5.

#### 7.3.1 Bladder Diary

A 7-day bladder diary will be completed by subjects (with the caregiver's assistance if necessary) at Screening and regularly throughout the study to record the following parameters:

- Weekly number of UI episodes
- Daily urinary frequency (total, spontaneous void only, CIC only)
- 24-hour voided volume (total, spontaneous void only, CIC only)
- Volume per void (total, spontaneous void only, CIC only).

Refer to

Bladder Diary Usage

Bladder Diary Usage

for full details regarding bladder diary usage.

## 7.3.2 Urodynamic Examination

#### 7.3.2.1 Subjects in the Urodynamic Subset

Subjects in the urodynamic subset will undergo a standardised urodynamic (filling cystometry) assessment at Screening and again at Week 6 following each IMP administration.

Urodynamics will be conducted according to International Continence Society recommendations [20]. Full details of the urodynamic procedures including standardisation, training, equipment setup, subject preparation, trace annotations, calculations and central review process are contained in a separate Study Specific Urodynamic Manual.

All urodynamic procedures will be covered with a minimum of 2 days of appropriate prophylactic antibiotics. See Section 6.4.1.2 for further details on antibiotic prophylaxis in the study.

All urodynamic data will be reviewed by independent central reviewers to determine the final values for the urodynamic parameters. The central reader's determination will be used for analysis purposes.

During Screening the site will determine if the subject has NDO via the presence of IDCs (inclusion criterion #16); without confirmation from the central reader.

The following urodynamic parameters will be obtained (Table 20):

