**PAGE 34/139** 

### 3 STUDY DESIGN

# 3.1 General Design and Study Schema

This is a phase III, multicentre, randomised, double blind, parallel group, placebo controlled study to assess the efficacy and safety of two doses of Dysport® (600 U and 800 U) in adult subjects with SCI or MS with UI due to NDO, who have not been adequately managed with oral medication and who routinely require CIC to manage their bladder function. The study will be conducted at approximately 90 study sites and 330 subjects are planned.

This study has two treatment periods:

- A double blind placebo controlled period, where subjects receive a single IMP treatment administration of either 600 U or 800 U Dysport® or placebo
- A subsequent double blind active treatment period, where subjects can receive multiple active IMP retreatment administrations of either 600 U or 800 U Dysport®. This second period commences when subjects receive their first study retreatment.

There is significant variability of local clinical practice in conducting urodynamic (filling cystometry) assessments. Due to the difficulties in standardising and performing study specific urodynamics in a global program, this study will include sites that are unable to alter their local site practice sufficiently to perform standardised urodynamics. The study therefore has two subsets:

- Urodynamic subset (planned ≥200 subjects)
  - All subjects in this subset must have standardised urodynamics (as described in the Study Specific Urodynamic Manual) during Screening and at Week 6 following each study treatment
  - o Screening standardised urodynamics must confirm the presence of NDO
- Non-Urodynamic subset
  - All subjects in this subset must have documented urodynamic proven NDO in the 12 months prior to Screening. If not, then urodynamics must be performed per local practice during Screening to confirm the diagnosis of NDO
  - o Urodynamics will not be performed in the post-screening period in this subset

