3.2 Secondary Efficacy Endpoints

The secondary efficacy endpoints are divided into those that relate to parameters measured in the bladder diary, those measured by urodynamic filling cystometry and those that are quality of life measures. From these secondary measures, there are two that have been selected to be analysed as part of a hierarchical testing scheme see Section 3.2.1.

Bladder diary measures:

Mean change from study baseline to post-treatment timepoints in the following variables:

- weekly number of UI episodes (except for week 6 after Treatment 1 which is the primary efficacy endpoint)
- total daily urinary frequency (spontaneous void and CIC)
- daily spontaneous voiding frequency
- daily CIC frequency
- total 24-hour voided volume (spontaneous void and CIC)
- 24-hour voided volume (spontaneous void only)
- 24-hour voided volume (CIC only)
- total volume per void (spontaneous void and CIC)
- volume per void (spontaneous void only)
- volume per void (CIC only)

Proportion of subjects with:

- no episodes of UI (i.e. 100% improvement where continence is achieved)
- UI response at several levels (i.e. $\geq 30\%$ improvement, $\geq 50\%$ improvement, $\geq 75\%$ improvement)

Urodynamic filling cystometry measures (urodynamic subset only):

Mean change from study baseline to week 6 after Treatment 1 in the following variables:

- MCC
- MDP during storage
- Vol@1stIDC (subjects without a post-treatment IDC will have their Vol@1stIDC imputed from their MCC)
- maximum detrusor pressure at first involuntary detrusor contraction (PdetMax@1stIDC)

- end fill pressure (EFP)
- detrusor compliance (DC)

Proportion of subjects with:

- No IDCs (i.e. urodynamic cure is achieved)

Patient-reported outcome questionnaires:

Mean change from study baseline to post-treatment timepoints in the following variables:

- I-QoL total summary score
- I-QoL Score of domain: Avoidance and limiting behaviour
- I-QoL Score of domain: Psychosocial impact
- I-QoL Score of domain: Social embarrassment
- EuroQol 5-dimension 5-level (EQ-5D-5L): Total descriptive score
- EQ-5D-5L: self-rated health (VAS)
- modified patient global impression - improvement (mPGI-I) score (to be assessed at each timepoint without comparison to baseline)

Duration of effect following the first and subsequent treatments

- time to request retreatment
- time to eligibility for retreatment
- time between treatments.

Detailed definitions of all efficacy endpoints are presented in [Appendix II](#).

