5.6 Urodynamic Population

All subjects in the mITT population included in the urodynamic subset at randomisation.

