6.2 Handling of Dropouts or Missing Data

6.2.1 Analysis Endpoints

6.2.1.1 Efficacy Endpoints

Refer to Section 3.1 and 3.2 for the list of primary and secondary efficacy endpoints and Section 3.2.1 for the list of secondary endpoints used in the hierarchical analysis.

Bladder diary: For data collected from the 7-day bladder diary, if there is 1 or 2 days with no data, the arithmetic means recorded (on the 5 or 6 days that do have events recorded) from the bladder diary parameters will be used for the days with no recorded bladder diary data. If there are more than 2 days of missing data, then the 7-day bladder diary data will be considered invalid.

Statistical Analysis Plan

Version: Final v1.0
September-2018

Ipsen Protocol No. D-FR-52120-223
000000146513

Date of Issue: 21-

Covance Study ID:

Primary efficacy endpoint: No imputation is planned for the primary analysis of the primary endpoint. A sensitivity analysis of the primary efficacy endpoint will be performed using multiple imputations (MI) for missing or invalid data (see Section 7.6.4.3).

Urodynamic secondary efficacy endpoints: All urodynamic data will be reviewed by independent central reviewers to determine the final values for the urodynamic parameters. Only the central reader urodynamic values will be used for analysis purposes. For the secondary efficacy endpoint of Vol@1stIDC, subjects who do not exhibit a post-treatment IDC after the first IMP administration will have Vol@1stIDC imputed using the recorded corrected MCC volume at that post-treatment visit.

Quality of life secondary endpoints: For I-QoL total summary score, in accordance with the I-QoL User's Manual (US English version, March 2013), if no more than three items are omitted, a normal arithmetic mean substitution will be computed for these omitted items and imputed to calculate the total summary score. If more than three items are omitted, then there will be no more imputation for those omitted items, and the total summary score will be missing. Similarly, this rule will be applied for each of the domain scores (avoiding and limiting behavior, psychosocial impact, and social embarrassment). These derived scores will be used for analysis, and the investigator recorded eCRF I-QoL total summary score, and each recorded domain score will only be listed.

The formula for the derived scale scores is as follows:

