7.6.6.2 Urodynamic Filling Cystometry Parameters

See Section 3.2 for list of urodynamic endpoints.

The summary tables for mean values at Week 6 and the mean change from study baseline for the DBPC cycle, and for the Dysport Cycles (i.e. Dysport Cycle 1, Dysport cycle 2 ...) will be presented using descriptive statistics for continuous endpoints. For each of the “mean change” at Week 6 urodynamic parameters, an ANCOVA model will be fitted using the “mean change” endpoint, as the response variable to obtain the p-value of treatment groups. The model will be the same as the sensitivity analyses for the primary efficacy endpoint in 7.6.4.2. The LSMEANS of the mean change from study baseline at Week 6 in each group with standard error, the difference of mean between the two treatment groups, the 95% CI of the difference and the p-value for treatment group will be presented.

Number and percentage of subjects with no IDC will be also summarised. A logistic regression model will be performed with “proportion of subjects” as the response variable. The model will include treatment group, and stratification variables.

Odds ratio, 95% CI of odds ratio, and p-value will be presented.

The SAS codes of logistic regression for reference are below.

CCI
[Redacted SAS code block]

In above codes, the variables are defined as:

Statistical Analysis Plan

Version: Final v1.0

Date of Issue: 21-

September-2018

Ipsen Protocol No. D-FR-52120-223

Covance Study ID:

000000146513

CCI

Line plots of the LS means of changes will be plotted for MCC, MDP, Vol@1stIDC. In addition, a bar chart for the proportion of subjects with no IDC at Week 6 will be plotted.

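### Urodynamic cure has no visible baseline condition: a subject admitted on the site's reading but IDC-free on the central baseline reading can be scored as cured

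*Protocol*

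**What the plan says.** - **Entry.** Protocol 3.1 sets the rule for the urodynamic subset: "Screening standardised urodynamics must confirm the presence of NDO". Protocol 7.3.2.1 says who applies it: "the site will determine if the subject has NDO via the presence of IDCs", and this is done "without confirmation from the central reader".
- **Data analysed.** Protocol 7.3.2.1: "The central reader's determination will be used for analysis purposes". SAP 6.2.1.1: "Only the central reader urodynamic values will be used for analysis purposes". Protocol Table 20 lists presence of IDCs among the urodynamic parameters.
- **Population.** SAP 5.6: "All subjects in the mITT population included in the urodynamic subset at randomisation". Protocol 9.1 has the same definition. SAP 7.1 takes the analysis population as the denominator for percentages, unless the table shells say otherwise.
- **Endpoint.** Protocol 3.2.2.1 and Table 19, and SAP 3.2, define urodynamic cure as the absence of IDCs on the post-treatment assessment. None of them adds a condition on the baseline trace.
- **Model.** SAP 7.6.6.2 fits a logistic regression for this endpoint: "The model will include treatment group, and stratification variables". It has no baseline IDC term.
- **Status.** Protocol 9.6 places the no-IDC proportion fourth in an ordered urodynamic hierarchy. SAP 7.6.6 treats every secondary endpoint outside its two-endpoint hierarchy as exploratory, and this is one of them.

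**The concern.** Cure implies a move from IDC present to IDC absent. The plan uses one reader to establish that there was something to cure and another to decide whether it has gone. Where the two disagree at baseline, the subject has nothing to lose on the analysed scale. If the Week 6 trace is also IDC-free, the subject is a cure with no change.

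Disagreement is foreseeable. The protocol lets the central determination replace the site's for analysis. Protocol 7.3.2.2 also plans retrospective central confirmation of NDO for the non-urodynamic subset, whose traces are not otherwise analysed, and states no such step for the subset whose IDC data are analysed.

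At stake are the absolute cure rates, which would be too high in every arm, and the treatment contrast, which would be too small. A related silence concerns Vol@1stIDC: substitution from MCC is given only for subjects without a post-treatment IDC, so a subject with no centrally read baseline IDC has no baseline value for it.

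**Working it through.** **The plan's own figure.** No figure is given for the no-IDC endpoint. The only one for this subset is the size of 200, set for MCC in Protocol 9.6 (difference 104.5 mL, SD 212.9 mL, power 90%, alpha 0.05, two-sided by Protocol 9.3). With both doses pooled 2:1 against placebo, the placebo group needs 1.5 × (1.960 + 1.282)² × 212.9² / 104.5² = 65.4, so 66, and the total is 66 + 132 = 198. That reproduces the planned 200. Spread over three groups, 200 gives about 67 per arm, which is used below.

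**Tracing one subject through the rules.**
1. The site sees an IDC at Screening, and the subject enters the subset.
2. The central reader scores the same trace as IDC-free. That is the analysed baseline.
3. The subject is randomised and treated, and so is in the urodynamic population.
4. The central reader finds no IDC at Week 6.
5. The endpoint counts a cure. Neither the denominator nor the model removes or adjusts for this subject.

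**Size, on assumed inputs.** Let f be the share with no centrally read baseline IDC, s the chance that such a subject is IDC-free at Week 6 (taken as equal in all arms), and p the true cure rate among subjects with a baseline IDC. Then:

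- observed rate = f·s + (1 − f)·p
- observed difference = (1 − f) × true difference, whatever the value of s

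With p = 45% on Dysport and 10% on placebo, the true odds ratio is (0.45/0.55)/(0.10/0.90) = 7.4.

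| f | s | Dysport | Placebo | Odds ratio |
|---|---|---|---|---|
| 5% | 50% | 45.3% | 12.0% | 6.1 |
| 10% | 50% | 45.5% | 14.0% | 5.1 |
| 15% | 50% | 45.8% | 16.0% | 4.4 |
| 5% | 90% | 47.3% | 14.0% | 5.5 |
| 10% | 90% | 49.5% | 18.0% | 4.5 |
| 15% | 90% | 51.8% | 22.0% | 3.8 |

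Example: at f = 10% and s = 90%, placebo = 0.10 × 0.90 + 0.90 × 0.10 = 18.0% and Dysport = 0.10 × 0.90 + 0.90 × 0.45 = 49.5%.

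**Power**, one dose against placebo, two-sided 0.05: Φ(|ln OR|/SE − 1.96), where SE² is the sum of the reciprocals of the four expected cell counts. True rates 35% against 10%, f = 10%, s = 90%:

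- No disagreement, 67 per arm: ln OR 1.578, SE 0.481, power 90.7%.
- As the plan reads, 40.5% against 18.0%, 67 per arm: ln OR 1.132, SE 0.404, power 80.0%.
- With the fix, 35% against 10%, 67 × 0.9 = 60.3 per arm: ln OR 1.578, SE 0.507, power 87.5%.

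With 45% against 10% and the same f and s, the last two become 96.2% and 97.9%.

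**The case against.** The best answer is that the deciding text may be withheld. SAP 3.2 refers to Appendix II for detailed endpoint definitions, and that appendix is redacted, as are the logistic code and its variable definitions in SAP 7.6.6.2. The wording of inclusion criterion 16 is not visible, the central review process sits in a separate urodynamic manual, and the table shells may change a denominator. A reader might infer that the plan has no baseline condition at all. The documents do not support that; they show only that none appears in the readable population, endpoint, denominator and model. This stands, and the fix is worded accordingly.

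Four further points also stand.

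- **Direction.** A reader might infer a bias in favour of Dysport. Entry is decided before randomisation and the central readers are independent, so the disagreement should be similar across arms. If treatment has no effect, observed rates are equal too, so type I error is not inflated. With a real effect, the contrast shrinks.
- **Timing of the central read.** It is tempting to say that the baseline reading is made before treatment. Only the trace is known to predate it; the documents do not say when it is read. Restricting the analysis on that reading is safe if the reader is blind to allocation, which should be stated.
- **Power.** The fall from 91% to 80% is not all recoverable, because the fix also removes 10% of subjects. With large effects there is little to recover.
- **Vol@1stIDC.** A reader might infer that this analysis needs a new denominator. A subject without a baseline value has no change score and no covariate for the ANCOVA, so that subject already drops out. Only a statement is needed.

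It can also be argued that the endpoint is simply absence of IDCs, with cure as a label, and that analysing the whole randomised subset is legitimate. It is, as a sensitivity analysis. But while the result is reported as cure, the main analysis should require something to cure. Table 19 plans presence of IDCs at baseline as well as at Week 6, so the data are available.

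**Conclusion.** The concern holds on the readable text, as a definitional gap of moderate importance. Site-read entry, centrally read outcome, a whole-subset denominator and no baseline condition together let a subject with no centrally read baseline IDC be scored as cured. The effect is inflated cure rates in all arms and a diluted odds ratio.

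The size cannot be taken from the documents, because neither a disagreement rate nor a cure rate is given. Across f of 5–15% and s of 50–90%, with true cure of 45% against 10%, the odds ratio falls from 7.4 to between 6.1 and 3.8, and placebo cure reads 12–22% instead of 10%. The gain in power from the fix depends on the scenario: about 80% to 87.5% in one, about 96% to 98% in the other.

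The primary endpoint and the two main hierarchical secondary endpoints are unaffected. The SAP treats this endpoint as exploratory, although Protocol 9.6 lists it in a urodynamic hierarchy; the two documents should be reconciled separately.

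**What to change.** First check Appendix II. Unless it already contains the condition:

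1. In SAP 3.2 and 7.6.6.2, define urodynamic cure as at least one IDC on the central reading of the baseline trace and none on the central reading at Week 6. Use as denominator the urodynamic-population subjects with a centrally read baseline IDC.
2. State that the central baseline reading is made blind to treatment allocation.
3. Report by arm the number of subjects with no centrally read baseline IDC.
4. State that these subjects have no baseline Vol@1stIDC and so drop out of that analysis.
5. Keep the all-subset proportion as a sensitivity analysis.

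The cost is SAP wording and one extra tabulation. No new data are needed, since Protocol 7.3.2.1 already sends all urodynamic data in this subset to central review. The downside is a slightly smaller denominator for this one endpoint, for example about 60 instead of 67 per arm at 10% disagreement.
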